9.2 Study day / study treatment day

Day 1 is the day of start of study intervention, the day before is Day -1 (no Day 0 is defined). Study day is defined relative to Day 1.

9.3 Definition of duration and ‘time since’ variables

Durations in days will be calculated by the difference of start and stop date + 1 (e.g. duration of AE (days) = end date of AE – start date of AE + 1) if not otherwise specified.

9.4 Conversion factors

The following conversion factors will be used to convert days into months or years:

$$1 \text{ week} = 7 \text{ days}, 1 \text{ month} = 30.4375 \text{ days}, 1 \text{ year} = 365.25 \text{ days}.$$

9.5 Imputation of missing data

Unless otherwise specified all data will be evaluated as observed, and no imputation method for missing values will be used.

In all participant data listings, imputed values will be presented and imputed information will be flagged.

Missing statistics, e.g. when they cannot be calculated, should be presented as not determined “nd”. For example, if n=1, the measure of variability (SD) cannot be computed and should be presented as “nd”.

For the classification as treatment-emergent and calculation of duration, incomplete AE-related dates will be handled as described below. The incomplete dates without imputation will be presented in listings.

There will be no imputation for missing or incomplete dates for prior or concomitant medications or procedures.

Adverse events	
For the classification as treatment-emergent and calculation of duration, incomplete AE-related dates will be imputed as follows:
 
• If the AE onset date is missing completely, then the onset date will be replaced by the start of study treatment.• If only the day part of the AE onset date is missing, but the month and year are equal to the start of study intervention, then the AE onset date will be replaced by the start of study intervention. For example, if the AE onset date is --/JAN/2015, and study intervention start date is 15/JAN/2015, then the imputed AE onset date will be 15/JAN/2015. If the end date or resolution date indicates that the AE has stopped before start of study intervention, this date will be used for imputation instead of start of study intervention date.• If both the day and month of the AE onset date are missing but the onset year is equal to the start of study intervention, then the onset date will be replaced by the start of study intervention. For example, if AE onset date is --/---/2014, and study intervention start date is 19/NOV/2014, then the imputed AE onset date will be 19/NOV/2014.• In all other cases the missing onset day or missing onset month will be replaced by 1.• Incomplete stop date will be replaced by the last day of the month (if day is missing only), if not resulting in a date later than the date of participant's death. In the latter case the date of death will be used to impute the incomplete stop date.• In all other cases the incomplete stop date will not be imputed. If stop date of AE is after date of cut-off this date will be kept.
Previous and concomitant medication	For identification of previous or concomitant medications/procedures, no formal imputation will be performed on missing or incomplete dates. Rules presented in Table 2 will be used to define if a medication/procedure is considered as a previous, concomitant or both previous and concomitant medication/procedure.

Table 1 Stopping rules for medication/procedure end dates

End date of medication/procedure			Stopping rule
Day	Month	Year	
UNK	UNK	UNK	After treatment start (ongoing)
UNK	UNK	< Treatment start (year)	Before treatment start
UNK	UNK	≥ Treatment start (year)	After treatment start
		< Treatment start (month and year)	Before treatment start
UNK		≥ Treatment start (month and year)	After treatment start
		< Treatment start (complete date)	Before treatment start
		≥ Treatment start (complete date)	After treatment start

UNK = Unknown

Table 2 Rules to define previous and/or concomitant medications

Start date of medication/procedure			Stopping rule	Medication/procedure
			Table 1)	
Day	Month	Year		
UNK	UNK	UNK	Before treatment start	Previous
UNK	UNK	UNK	After treatment start	Previous and concomitant
UNK	UNK	≤ Treatment start (year)	Before treatment start	Previous
UNK	UNK	≤ Treatment start (year)	After treatment start	Previous and concomitant
UNK	UNK	> Treatment start (year) and ≤ Treatment end [+ 30] days (year)	After treatment start	Concomitant
UNK		≤ Treatment start (month and year)	Before treatment start	Previous
UNK		≤ Treatment start (month and year)	After treatment start	Previous and concomitant
UNK		> Treatment start (month and year) and ≤ Treatment end [+ 30] days (month and year)	After treatment start	Concomitant
≤ Treatment start (date)			Before treatment start	Previous
≤ Treatment start (date)			After treatment start	Previous and concomitant
> Treatment start (date) and ≤ Treatment end [+ 30] days (date)			After treatment start	Concomitant

UNK = Unknown

Dates of study intervention	No imputation will be done.
-----------------------------	-----------------------------

10 Study Participants

The subsections in this section include specifications for reporting participant disposition and study treatment/study discontinuations. Additionally, procedures for reporting protocol deviations are provided.

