### **8.3.1 Time Period and Frequency for Collecting Adverse Event and Serious Adverse Event Information**

- All SAEs will be collected from the signing of the ICF until the Follow-Up Visit/Discontinuation Visit at the time points specified in the SoA (Section 1.3). Beyond this reporting period, any new unsolicited SAEs that the Investigator spontaneously reports to the Sponsor will be collected and processed.
- All AEs will be collected from the signing of the ICF until Follow-Up Visit/Discontinuation Visit at the time points specified in the SoA.
- AEs/SAEs that begin before the start of study intervention but after obtaining ICF will be recorded on the Medical History/Current Medical Conditions CRF, not on the AE CRF.
- All SAEs will be recorded and reported to the Sponsor or designee immediately and under no circumstance will this exceed 24 hours, as indicated in [Appendix 4](#). The Investigator will submit any updated SAE data to the Sponsor within 24 hours of it being available using the same procedure that was used for the initial report.
- Investigators are not obligated to actively solicit AEs or SAEs after the end of study participation. However, if the investigator learns of any SAE, including a death, at any time after a participant has been discharged from the study, and he/she considers the event to be reasonably related to the study intervention or study participation, the Investigator will promptly notify the Sponsor.

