15.1 Adverse Events

Treatment-emergent adverse events (TEAEs) are those events that begin or that worsen in severity after at least one dose of the study intervention has been administered.

Adverse events related to study treatment are those events with relationship missing, unknown or related.

AEs will be coded using the most recent MedDRA version at time of database lock.

All analyses described in Section 15.1 will be based on TEAEs if not otherwise specified. The AE listings will include all AEs (whether treatment-emergent or not). Non TEAEs will be flagged in the listings.

Unless otherwise specified, TEAEs will be summarized by number and percentage of participants with the TEAE in the category of interest, by hepatic function group, primary SOC and PT in decreasing frequency.

Each participant will be counted only once within each SOC or PT. If a participant experiences more than one AE within a SOC or PT for the same summary period, only the AE with the strongest relationship or the worst severity, as appropriate, will be included in the summaries of relationship and severity.

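### Two of the three AE onset rules that impute to the dosing date ignore a recorded pre-dose end date, so an event already over can be classed as treatment-emergent

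*SAP*

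**What the plan says.** SAP 9.5 gives four onset rules for adverse events, used to classify events as treatment-emergent and to calculate duration.

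- **Completely missing:** "If the AE onset date is missing completely, then the onset date will be replaced by the start of study treatment". No condition on the end date follows.
- **Day missing:** "If only the day part of the AE onset date is missing, but the month and year are equal to the start of study intervention", the onset becomes the dosing date. This rule adds an exception: "If the end date or resolution date indicates that the AE has stopped before start of study intervention, this date will be used for imputation".
- **Day and month missing:** "If both the day and month of the AE onset date are missing but the onset year is equal to the start of study intervention", the onset again becomes the dosing date. There is no exception.
- **Catch-all:** otherwise the missing day or month is set to 1.

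No general sentence extends the end-date exception beyond the day-missing rule.

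SAP 15.1 gives the definition: "Treatment-emergent adverse events (TEAEs) are those events that begin or that worsen in severity after at least one dose of the study intervention" has been given. It looks at onset and worsening only, so it would not remove an event on the strength of its end date. SAP 9.3 gives the duration: "Durations in days will be calculated by the difference of start and stop date + 1".

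Protocol 8.3.1 sets the collection window: "All AEs will be collected from the signing of the ICF until Follow-Up Visit/Discontinuation Visit". It also directs events that begin after consent but before dosing to the Medical History/Current Medical Conditions page and not the AE page.

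**The concern.** Treating an event as treatment-emergent when its timing is unknown is a sensible default. It stops being sensible when the end date settles the matter, because an event that was over before dosing can neither have begun nor worsened after it. As written, the two unprotected rules override an observed date.

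They also disagree with the SAP's own approach in two places. The day-missing rule makes the check. For medications, Table 2 of SAP 9.5 classes a wholly unknown start date with a stop before treatment as previous, so there the stop date decides.

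Occurrence of treatment-emergent events is a secondary endpoint, and the tables in SAP 15.1 are built on this classification. Planned groups are of 8, with up to 4 more in Group 1, so a single event can show in the percentages.

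**Working it through.** **Inputs.** The onset rules of SAP 9.5; the SAP 9.3 formula, duration = end date - onset date + 1; planned group sizes from Protocol 9.2 (8 per group, Group 1 up to 12). One assumption: an imputed onset on the dosing date counts as treatment-emergent, which is the evident purpose of imputing to that date.

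**The SAP's own examples.** Onset --/JAN/2015 with dosing on 15/JAN/2015 gives 15/JAN/2015. Onset --/---/2014 with dosing on 19/NOV/2014 gives 19/NOV/2014. Applying the rules as written reproduces both.

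**Events that ended before dosing.** Take dosing on 19/NOV/2014 and an event that ended k days earlier. Under the completely-missing and day-and-month-missing rules the onset is the dosing date, so duration = -k + 1, which is 0 or less for every k of 1 or more. Under the day-missing rule the onset is the end date, so duration = 0 + 1 = 1.

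| End date | k | Completely missing, or day and month missing | Day missing |
|---|---|---|---|
| 18/NOV | 1 | treatment-emergent, -1+1 = 0 days | not treatment-emergent, 1 day |
| 17/NOV | 2 | treatment-emergent, -2+1 = -1 | not treatment-emergent, 1 day |
| 14/NOV | 5 | treatment-emergent, -5+1 = -4 | not treatment-emergent, 1 day |
| 09/NOV | 10 | treatment-emergent, -10+1 = -9 | not treatment-emergent, 1 day |
| 01/NOV | 18 | treatment-emergent, -18+1 = -17 | not treatment-emergent, 1 day |
| 22/OCT (Day -28) | 28 | treatment-emergent, -28+1 = -27 | does not apply: a November onset cannot end in October |

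**Partial end dates.** SAP 9.5 sets a stop date that lacks only its day to the last day of the month. A stop of --/OCT/2014 becomes 31/OCT/2014, which is 19 days before dosing. The two unprotected rules then give -19+1 = -18 days and the same wrong class.

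**Catch-all rule.** A search over onsets from 400 days before dosing up to the dosing date, with every end date from onset to the day before dosing, found no case in which this rule made a pre-dose-ended event treatment-emergent or gave a duration below 1.

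**Size.** One participant wrongly counted, who has no other treatment-emergent event, adds 1/8 = 12.5 percentage points to a group's overall incidence, or 1/12 = 8.3 points if all four optional Group 1 participants are added.

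**With the check extended to all three rules.** Every tested case (k = 1, 2, 5, 10, 18, 28) becomes not treatment-emergent with a duration of 1 day.

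**The case against.** The best case against the point is that hardly any event can reach the faulty rules. The error needs a recorded end before dosing, and an event that ended before dosing must also have begun before it. The site can therefore apply the Protocol 8.3.1 routing from the end date alone, even with no onset date, and the event never reaches the AE page. The data pattern is also odd: screening starts no earlier than Day -28, participants are asked about changes at each visit, and yet the onset month would have to be unknown while the end is known well enough to precede dosing. Queries are resolved and a data review meeting is held before lock. SAP 9.5 lists incomplete AE dates without imputation, so a reviewer could see a pre-dose end beside a blank onset.

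Most of this stands, and it is why the point is minor. It does not close the route. Protocol 8.2.1 puts new examination findings after consent on the AE form, and the Schedule of Activities has a full examination on Day -1. SAP 15.1 expects events that are not treatment-emergent in the AE listings and flags them. The check in the day-missing rule itself presupposes that events which ended before dosing can be in the data. Nor does confinement cover the window: AEs are collected from consent, but hospitalization starts only on Day -1.

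A reader might infer that the treatment-emergent tables are unreliable, or that impossible durations will appear in reported summaries. The documents support neither. The routing rule keeps the expected number of cases very small, and SAP 15.1 plans no summary of AE duration.

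**Conclusion.** The rule is wrong as written, but the consequence is small. Two of the three onset rules that impute to the dosing date can class an event as treatment-emergent against its own recorded end date and give it a duration of 0 or less. It would be too strong to say that every onset rule fails: the day-missing rule is protected, and no failure was found in the catch-all rule.

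The 12.5 and 8.3 point figures are what one case would do to overall incidence, and only if that participant has no other treatment-emergent event. They are not a forecast; the documents give no basis for estimating how often such dates occur, and with compliant data entry there may be none. The primary endpoints, AUC from zero to infinity and Cmax, do not depend on this rule.

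**What to change.** In SAP 9.5, take the end-date exception out of the day-missing rule and state it once for every rule that imputes onset to the dosing date: if the end date, including one completed by the SAP's own stop-date rule, shows that the event stopped before the start of study intervention, the end date is used as the imputed onset. Such events are then flagged as not treatment-emergent.

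The cost is one sentence and one programming condition. There is one small drawback: the imputed duration becomes 1 day whatever the true length, as already happens under the day-missing rule.

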10.1 Disposition of Participants and Discontinuations

The number and percentage of participants in each of the below disposition categories will be presented by hepatic function group and total, where applicable. Percentages will be presented with respect to the number of treated participants.

- Total number of participants screened (i.e. participants who gave informed consent)
- Number of participants who discontinued from the study prior to treatment overall and grouped by the main reason (e.g. the failed specific inclusion or exclusion criteria, withdrawal of consent, Other (COVID-19-related and COVID-19-non-related))
- Number and percentage of treated participants
- Number and percentage of treated participants who completed study treatment

Individual listings for study termination and analysis populations will be presented.

The number and percentage of participants in each analysis population will be presented by hepatic function group and total. Percentages will be presented with respect to the number of treated participants.

10.2 Protocol Deviations / Exclusion from Analysis Sets

10.2.1 Important Protocol Deviations

Important protocol deviations (IPDs) are protocol deviations that might significantly affect the completeness, accuracy, and/or reliability of the study data or that might significantly affect a participant's rights, safety, or well-being.

Important protocol deviations include:

- Participants enrolled and dosed on the study who did not satisfy enrolment criteria
- Participants that develop withdrawal criteria whilst on the study but are not withdrawn
- Participants that receive the wrong study treatment or an incorrect dose
- Participants that receive an excluded concomitant medication
- Failure to collect data necessary to interpret primary endpoints
- Failure to collect necessary key safety data
- Deviation from Good Clinical Practice (GCP)

- Any other protocol deviation that might significantly affect the completeness, accuracy, and/or reliability of the study data or that might significantly affect a participant's rights, safety, or well-being.

Important protocol deviations will be identified for all participants by either site monitoring, medical review processes or programming and confirmed prior to or at the Data Review Meeting at the latest.

All important protocol deviations are documented in SDTM datasets whether identified through site monitoring, medical review or programming.

Important protocol deviations will be summarized for:

- Deviations from the inclusion and exclusion criteria
- Deviations post inclusion

All important protocol deviations will be listed by participant. Minor protocol deviations related to COVID-19 will also be listed by participant.

Participants may be excluded from the PK analysis population if they have an AE of vomiting that occurs at or before 2 times median t_{max} of the group.

10.2.2 Reasons Leading to the Exclusion from an Analysis Set

A frequency table organized according to reason for exclusion from the PK analysis population, as well as a listing, will be provided.

11 Demographics and Other Baseline Characteristics

If not stated otherwise, the following analyses will be performed based on the safety analysis population by hepatic function group and total.

11.1 Demographics

Demographic characteristics and physical measurements will be summarized descriptively using the following information from the Screening Visit eCRF pages.

- The following demographic characteristics will be included:
 - Sex: male, female
 - Race: white, black or African American, Asian, American Indian or Alaska Native, Native Hawaiian or Other Pacific Islander, other, not collected at this site, unknown
 - Ethnic origin: Hispanic or Latino/Not Hispanic or Latino, Japanese/Not Japanese
 - Age (years)
 - Weight (kg) at Screening

- Height (cm) at Screening
- BMI (kg/m²) at Screening

Specifications for computation:

- Age [years]
 - (date of given informed consent - date of birth + 1) / 365.25 Note: Alternatively, Day 1, i.e. day of start of study treatment, may be used instead of the day of given informed consent.
 - In case of missing day for at least one date, but month and year available for both dates:
For the derivation of age, the day of informed consent and the day of birth will be set to 1 and the formula above will be used
 - In case of missing month for at least one date, but year available for both dates:
For the derivation of age, the day and the month of informed consent and the day and month of birth will be set to 1 and the formula above will be used
- BMI [kg/m²] =
$$\frac{\text{weight [kg]}}{\text{height[cm]}^2} \times 10000$$

11.2 Medical History

The medical history will be coded using the most recent MedDRA version at time of database lock.

Medical history will be listed by participant and will include the following: description of disease/procedure, MedDRA system organ class (SOC), MedDRA preferred term (PT), start date, end date (or ongoing, if applicable) and severity (if ongoing).

11.3 Other Baseline Characteristics

The albumin-bilirubin score is calculated as:

$$\text{albumin-bilirubin score} = [\log_{10} \text{Total Bilirubin } (\mu\text{mol/L}) \times 0.66] + [\text{Albumin } (\text{g/L}) \times -0.085]$$

The baseline albumin-bilirubin score is defined as the arithmetic mean of the screening and baseline (Day -1) values. The albumin-bilirubin score will be summarized descriptively at screening, Day -1 and baseline.

The De Ritis ratio is calculated as:

$$\text{De Ritis ratio} = \text{AST} / \text{ALT}$$

The baseline De Ritis ratio is defined as the arithmetic mean of the screening and baseline (Day -1) values. The De Ritis ratio will be summarized descriptively at screening, Day -1 and baseline.

Nicotine usage, alcohol consumption and caffeine consumption data will be listed.

Baseline characteristics with respect to vital signs, physical examinations, and hematology/biochemistry will be part of Section 15 (Safety Evaluation).

12 Previous or Concomitant Medications/Procedures

The following analyses will be performed based on the safety analysis population by hepatic function group.

Concomitant treatments are medications, other than study intervention, which are taken by participants from the time the participant signs the informed consent until completion of the study.

Previous medications are medications, other than study intervention, which started before first administration of study intervention.

A medication may be classified as both concomitant and previous. The respective flags will be derived based on start and end date.

Previous medications and concomitant treatments will be coded using the most recent WHO-DD version at time of database lock.

Previous medications and concomitant treatments will be listed by participant and include the following information: Medication name (trade name), generic name, WHO drug name (including ATC coding and PT), dose (and dose units), frequency, route of administration, start and end date/time, indication and origin (medical history, AE, disease related condition, prophylaxis or other). Duration will be calculated and included in the listing.

All **concurrent procedures**, which were undertaken during the on-treatment period will be listed according to the CRF page “Concomitant Procedures”. Concurrent procedures will be classified by medical review.

13 Study treatment: Compliance and Exposure

The following analyses will be performed based on the safety analysis population by hepatic function group.

No imputation of missing start dates of study treatments will be done.

Exposure to study intervention will be recorded in the eCRF. The listing of exposure to the study intervention will include the treatment, the hepatic function group, study intervention administered and date/time of administration.

14 Efficacy Analyses

Not applicable.

15 Safety Analyses

This section includes specifications for summarizing safety endpoints that are common across clinical studies such as adverse events, laboratory tests and vital signs.

Safety analyses will be done on the safety analysis population and according to the as-treated principle.

